Investigating the effects of cuing medication availability on patient-controlled analgesia pump usage in pediatric patients: Results of a randomized controlled trial

NCT02456909

Date of Document: March 30, 2015

Study Protocol and Statistical Analysis Plan

Materials and Methods

This single-center, prospective, RCT was conducted at a large children's hospital in the Midwest. The study was approved by the hospital Institutional Review Board, and was registered at www.clinicaltrials.gov (ID: NCT02456909) by the principal investigators prior to study enrollment. Enrollment was April 2015 – August 2017.

Participants

Potential participants between the ages of 7 – 17 years, undergoing an orthopedic, abdominal or thoracic surgery for which PCA is routinely prescribed for post-operative pain management, were identified from the hospital surgery schedule. Eligible patients were opioid naïve, and patients and at least one parent were able to read and speak English. Exclusion criteria included 1) prior experience with PCA, 2) cognitive delay precluding independent use of the PCA button, or 3) pre-operative use of a daily anxiolytic or antidepressant medication.

Procedures

Recruitment and Randomization

Patients were approached immediately prior to surgery. After informed consent and assent were obtained, participants were randomized into either the control group or the experimental “light” group and were stratified by gender and surgical procedure (orthopedic, abdominal, or thoracic) in blocks of 4. The randomization scheme was created by a statistician on the research team using Windows version 6.0 of “rand.exe” (<http://block-stratified-randomization.software.informer.com>). Participants were enrolled by the clinical research coordinator, who used the scheme to assign participants to groups after consent. Recruitment continued until each group included 60 completed participants (defined as having completed at least 24 hours of PCA use and completed assessment of the primary outcome). Carefusion

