Alaris™ PCA pumps were used for all patients. The PCA profile (i.e. configuration of the light cue operation) for both groups was set up by a nurse in the post-anesthesia care unit (PACU). The starting opioid dose is standardized, and was set up by the PACU nurse. For the control group, the PCA pump was used according to the hospital's standard operating procedures: The PCA emitted a "beep" with every button press, and the status of the green light on the button never changed (i.e., it remained continually lit). For the light group, the PCA pump was configured so that the PCA button only emitted a "beep" when a button press resulted in successful opioid delivery. The green light on the button flashed during opioid delivery, was darkened immediately after delivery and was illuminated at the end of the lockout period, indicating a dose was ready to be delivered. Treatment of side effects was determined by the floor nurse who was not a member of the study team. To ensure consistent messaging, patients and parents in both groups were given scripted instructions regarding PCA use. The patient and guardian were also given a printed copy of the instructions prior to surgery.

PCA monitoring and Pain assessments

Either morphine or hydromorphone (converted to morphine equivalents) was administered using PCA for both groups as prescribed by the anesthesia service. Using morphine equivalents, our standardized PCA orders are as follows: 20 mcg/kg for the PCA dose and basal (if used), 8 minute lockout, and a 120 mcg/kg hourly maximum.

Patients had continuous pulse oximetry. Pain and sedation scores were recorded every 2 hours for the first 24 hours, with a minimum of every 4 hours thereafter. PCA use, including injections (i.e. button presses resulting in delivered doses) and attempts (i.e. button presses during the lockout period), were documented hourly by a nurse who was not a member of the study team. If for some reason the nurse was unable to document the hourly number of

injections and attempts (e.g. busy with another patient), the following hour's data would reflect the previous 2 hours' worth of attempts and injections.

Data collection terminated when the PCA was discontinued, or up to 60 hours post-surgery, whichever came first. The study period was defined as beginning when the patient arrived in the Post-Anesthesia Care Unit (PACU) through Post-Operative Day (POD) 2.

Measures

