Pain scores: Pain scores were recorded from the time patients left the PACU until discontinuation of the PCA or through POD 2 (whichever came first) and were extracted from the EHR. Pain was assessed using the age appropriate, hospital approved pain scale. Children either used a 0-10 (0 = no pain, 10 = worst pain possible) numeric rating scale, or the 0-10 Faces Pain Scale-Revised [10].

PCA usage

The total number of hourly injections and attempts were extracted from the EHR.

State Anxiety

The Spielberger State-Trait Anxiety Inventory for Children (STAIC), state version, is a well-validated 20 item questionnaire used to assess anxiety about a current situation or impending event⁴. Each question begins with the stem “I feel...” and ends with 3 choices (e.g., “very calm,” “calm,” “not calm”). Respondents are instructed to consider “*how you feel right now.*” A total score is computed from a sum of the items, with scores ranging from 0 – 60. The STAIC was administered by the research coordinator once before surgery (POD 0) and once per day on POD 1 and POD 2. Elevated state anxiety was based on T-scores and was defined as ≥ 1 standard deviation above the mean.⁵

Power Analysis:

An *a priori* sample size calculation was based on the primary outcome. Rahman et al. examined patient satisfaction with pain relief for those randomized to pain management with PCA vs. intravenous boluses of analgesia titrated to patient comfort levels.⁶ Based on a 1-5 scale (1 = excellent, 5 = disappointing), the average pain relief rating for patients in the PCA group was significantly better at 2.0 (± 0.37) than the rating for patients in the control group at 3.0 (± 0.24). With a power of 80%, a type I error rate (alpha) of 0.05, and a two-tailed t test, 60 patients would have been needed in each group to detect a difference of at least 0.16 SD between the light and control groups.

Statistical Analysis

Modified intent-to-treat analyses included all randomized participants, with the exception of those who did not receive the allocated intervention, as shown in Figure 1. Means and standard deviations or median and interquartile range (IQR) when data were skewed, were used for continuous data, and categorical items were described using frequency statistics. A Chi-square test or a Fisher’s exact test was used to explore the relations between categorical variables, and bivariate correlations (Pearson correlation test) were used to explore correlations

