between continuous variables. Comparisons between intervention and control groups and between age groups [children (≤ 12 years) and adolescents (13-17 years)] were conducted using a Mann-Whitney test. Missing data were treated using listwise deletion, and assumed to be missing completely at random. A two-sided p-value <0.05 was used to define what was considered significant.

Multivariable analyses using a mixed model with random time were used to examine the effect of the intervention group and age group on two dependent variables (DV): 1) opioid consumption over time and, 2) injections:attempts ratio over time. The independent covariates (IV) considered were pain scores, methadone use and the interaction between methadone use and intervention group, age group, intervention group, and the interaction between age group and intervention group. A backward model selection procedure was used, with a p-value <0.05 as a criterion to keep the variable in the multivariable model. Based on this criterion, the interaction between intraoperative methadone and intervention group was dropped from the model. The DV opioid consumption was transformed using square root to satisfy model assumptions. The parameters were estimated using Maximum likelihood, and unstructured covariance structure was used for repeated measurements. The mixed model with random effects allows for missing data, under the assumption that data were missing at random. Statistical analyses were calculated using SPSS 24 (IBM SPSS Inc., Chicago, IL) and SAS 9.4 software (SAS Institute Inc., Cary, NC).

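### In the two secondary-outcome mixed models, the randomized group is subject to backward selection at p<0.05 with no stated exemption, and the text does not say how it was retained

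*Combined protocol and SAP*

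**What the plan says.** All of this is in the Statistical Analysis section unless noted.

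- **Purpose.** The mixed models were used to "examine the effect of the intervention group and age group on two dependent variables (DV"). The two outcomes are opioid consumption and the injections:attempts ratio, each over time.
- **Candidates.** Pain scores, methadone use and methadone by intervention come first in the list, followed by "age group, intervention group, and the interaction between age group and intervention group".
- **Keep rule.** "A backward model selection procedure was used, with a p-value <0.05 as a criterion to keep the variable in the multivariable model". No term is forced in, and nothing says that a main effect stays while its interaction stays.
- **Reported result.** "the interaction between intraoperative methadone and intervention group was dropped from the model". No other removal is mentioned. The final terms are not listed for either outcome, and the sentence speaks of one model although there are two.
- **Comparisons outside the selection.** Group and age-group comparisons "were conducted using a Mann-Whitney test".
- **Timing of pain.** Under Pain intensity, which is one of the Secondary Outcomes: "Pain scores were recorded from the time patients left the PACU until discontinuation of the PCA". Under Recruitment and Randomization, the PCA profile carrying the light cue "was set up by a nurse in the post-anesthesia care unit (PACU").

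**The concern.** A model built to estimate a randomized effect should report that effect whatever its p-value. Here the same threshold that screens covariates also decides whether the randomized term appears at all. Two things can follow. If the term fails the threshold, the reader gets no adjusted, over-time estimate or interval for the light cue. If it passes on its own p-value, the printed estimate has been filtered for being large, and its interval no longer has its nominal properties.

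These are the only adjusted, over-time analyses of opioid use and PCA behaviour in the plan, so the filter affects what can be concluded about both.

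A supporting issue concerns pain scores. They are measured after the cue is configured, and pain intensity is itself a secondary outcome. If the cue changes pain, a model that keeps pain scores may not estimate the total effect of assignment.

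**Working it through.** **Inputs.** From the documents: 60 completed participants per group (Recruitment and Randomization), a two-sided 0.05 threshold, and the six candidate terms. The Power Analysis addresses satisfaction only, so the plan has no figure for these two models to reproduce. It gives no true effect or variance for them either. The effects below are therefore assumed, in units of the SD of one summary value per patient.

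**Step 1: the survival threshold.** SE = √(2/60) = 0.183 SD. The term stays on its own p-value only if |estimate| > 1.96 × 0.183 = 0.36 SD.

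**Step 2: average estimate when kept.** For true effect d, let m = d/SE and c = 1.96.

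- P(kept) = 1 − Φ(c − m) + Φ(−c − m)
- Mean if kept = d + SE × [φ(c − m) − φ(c + m)] / P(kept)

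For d = 0.3: m = 1.643 and P(kept) = 0.376. The mean is 0.3 + 0.183 × (0.379 − 0.001)/0.376 = 0.484 SD, or 1.61 times the truth.

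**Step 3: the full rule, simulated.** Backward elimination on all six terms was run with 60 per arm, centred coding, true interactions of zero and 4,000 trials per cell, with and without hierarchy. Assumed effects were pain +0.3 per SD, methadone −0.3 and age group +0.3. It was run once with one value per patient, and once as a maximum-likelihood mixed model on three post-operative days with unstructured covariance and 26–28% of the last day missing. The ranges cover both.

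| Assumed true effect (SD) | Deleted, closed form | Mean if kept, closed form | Deleted, simulated | Mean if kept with no interaction, simulated | Mean if held in by age group × intervention, simulated |
|---|---|---|---|---|---|
| 0.2 | 80.5% | 0.454 | 71–82% | 0.46 | 0.19–0.20 |
| 0.3 | 62.4% | 0.484 | 55–65% | 0.49–0.50 | 0.29–0.32 |
| 0.5 | 21.8% | 0.569 | 21–24% | 0.57–0.58 | 0.49–0.52 |
| 0.8 | 0.8% | 0.804 | 1–2% | 0.81 | 0.80–0.82 |

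The last column applies under hierarchy with methadone × intervention dropped. When group survives with no interaction, its 95% CI covers the truth in 82–86% of such trials at 0.2 SD, 92–94% at 0.3 SD, and 95–96% at 0.5 and 0.8 SD.

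**Step 4: with group exempt.** A separate simulation with somewhat different assumed covariate effects forced group in and let selection act on the rest. In runs with no retained interaction, mean estimates were 0.00, 0.17, 0.30 and 0.50 SD for true effects of 0, 0.16, 0.30 and 0.50 SD.

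**Step 5: pain scores.** Assume a direct effect of 0.30 SD, a pain slope of 0.3 per SD, and a cue that lowers pain by 0.1, 0.3 or 0.5 SD. The total effect is 0.30 − 0.3 × reduction = 0.27, 0.21 or 0.15 SD. The pain-adjusted model returns about 0.30 each time, and its CI covers the total effect in 94–95%, 92% and 86–88% of trials. Without pain the model returns 0.27, 0.20–0.21 and 0.15, with coverage near 95%.

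**The case against.** The strongest reply is that the harm probably did not occur in the form the rule allows. The document is written in the past tense and reports a selection result. It names one interaction as dropped and says the models examined the intervention effect. The natural reading is that intervention group, and perhaps age group by intervention, stayed in. If that interaction held group in under hierarchy, the estimate is close to unbiased (last column of the table).

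This largely stands. A reader might infer that the randomized term was deleted, or that the reported effects are inflated; the documents support neither. What they leave open is the route: by design, through the interaction, or on its own p-value. Only the third carries the bias.

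A second reply is that the deletion rates mostly restate low power. That also stands. The unselected model without pain scores rejects in 33–35% of trials at 0.3 SD, so 65–67% are non-significant anyway, against 55–65% deleted. The rule does not create that uncertainty, but it withholds the estimate and interval that would show it.

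A third reply is that the sizes rest on assumptions. They do: effects, slopes and time unit are assumed, and neither hourly data nor the square-root scale was simulated. The direction of the bias does not depend on these choices.

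Finally, adjusting opioid use for concurrent pain can answer a legitimate, different question. That is a reason to label such a model, and it does not make it the main estimate of the cue's total effect. With a 0.1 SD change in pain, the difference is slight.

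**Conclusion.** The point holds as a gap in the selection rule and its reporting, confined to two secondary-outcome models. The rule as written can remove the randomized term. If the term is kept only on its own p-value, its estimate is biased away from zero on average over repeated trials, though not necessarily in this data set. At 60 per arm, an assumed 0.3 SD averages about 0.48 to 0.50 SD when kept. The bias is negligible near 0.8 SD, and small when a retained interaction holds the term in.

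A reader might extend this to the trial's main conclusion. The documents do not support that: the satisfaction outcome and the Mann-Whitney comparisons involve no selection. The latter, however, supply no adjusted estimate. The pain-score issue is valid but separate, and its size depends on how far the cue changes pain, which the plan does not give.

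This should be corrected. Confidence is medium because the final models are not shown.

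**What to change.** 1. State that intervention group is exempt from selection in both models, and report its estimate with a 95% CI whatever its p-value.
2. For the models already run, list the final terms for each outcome and say why group was retained.
3. Fix the other covariates in advance on subject-matter grounds. Decide on methadone in the same way, and do not let its observed use by arm settle whether it is included. The documents say "Patients were approached immediately prior to surgery" and that assignment followed consent. Assignment before intraoperative methadone is therefore likely, though no section times one against the other.
4. Show the intervention estimate without pain scores, and give the pain-adjusted model as a labelled sensitivity analysis.

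**Cost.** SAP wording and two refits. Leaving pain out costs a little precision: the SE rises from 0.184–0.185 to 0.191–0.192 with one value per patient, and from 0.183 to 0.189 in the mixed model. That is about 3–4%, under the assumed pain slope of 0.3 per SD. The change does not raise power, and an estimate that is read only when p<0.05 would still be inflated.

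### The two secondary-outcome mixed models use maximum likelihood with an unstructured covariance and no stated small-sample correction, so their standard errors run slightly small; report the final models by REML with Kenward-Roger

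*Combined protocol and SAP*

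**What the plan says.** The Statistical Analysis section of the combined protocol and SAP describes mixed models for "two dependent variables (DV): 1) opioid consumption over time and, 2) injections:attempts ratio over time". On estimation it says: "The parameters were estimated using Maximum likelihood, and unstructured covariance structure was used for repeated measurements". The models also carry a random time effect. Candidate terms are pain score, methadone, methadone by group, age group, group, and age group by group. Terms are kept or dropped by backward selection at 0.05, and the methadone-by-group term was dropped. The significance rule is: "A two-sided p-value <0.05 was used to define what was considered significant".

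The section names no REML fit, no degrees-of-freedom method and no small-sample adjustment. It does not say which test produced the selection p-values, or what the unit of time is. On numbers, Recruitment and Randomization says: "Recruitment continued until each group included 60 completed participants". That is about 120 children; the modified intent-to-treat set may be slightly larger. Under PCA monitoring and Pain assessments, follow-up ends at 60 hours or when PCA stops, if that is earlier, so fewer children contribute late data.

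**The concern.** Two mechanisms push the standard errors down. First, ML variance estimates do not allow for the degrees of freedom spent on fixed effects. Second, default standard errors treat the estimated covariance matrix as if it were known, and an unstructured matrix has many elements to estimate. REML addresses the first; the Kenward-Roger adjustment addresses the second as well.

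The bias runs one way, towards significance. In these models the p-values are used twice: they are reported for group, age group and their interaction, and they may also decide which terms survive selection. A borderline term, such as the age-by-group interaction, could be kept or called significant because of it.

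**Working it through.** **Stated figure.** The plan gives no standard error, degrees of freedom or type I error for these models, so there is nothing to reproduce on this point. Its one design figure, 60 per group, does reproduce: with pooled SD √((0.37² + 0.24²)/2) = 0.312 and a difference of 0.16 scale points, n = 2(1.960 + 0.842)² × 0.312²/0.16² = 59.6, so 60. (The Power Analysis labels the 0.16 as SD units, which is a separate matter.)

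**Inputs from the plan.** n = 120 (2 × 60), two-sided alpha 0.05, and the terms listed above. Child-level parameters: intercept, group, age group, age by group, methadone and methadone by group make 6; without the dropped interaction, 5. Pain score varies over time.

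**Assumed inputs.** The time unit, the within-child covariance, covariate prevalences and dropout (0% or 30%). The documents give none of these.

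**Step 1, closed form.** For a between-child effect, ML SE / REML SE = √((n − p)/n), and type I error = 2P(t > t_crit × ratio) on n − p degrees of freedom.
- p = 4: √(116/120) = 0.983, type I error 5.4%
- p = 6: √(114/120) = 0.975, type I error 5.6%
- p = 8: √(112/120) = 0.966, type I error 5.8%

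With a critical value of 1.96 in place of t, these become 5.6%, 5.9% and 6.1%.

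**Step 2, simulation under no group effect.** 120 children; fixed effects time, group, age group, group by age group, methadone and a time-varying pain score; unstructured covariance. Ranges cover t and normal critical values and, in the second row, two sets of runs.

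| Time points, dropout | Runs | ML SE / REML SE | ML SE / Kenward-Roger SE | Type I: ML | Type I: REML alone | Type I: REML + Kenward-Roger |
|---|---|---|---|---|---|---|
| 3, none | 4,000 | 0.978 | 0.962 | 5.9–6.1% | 5.5–5.8% | 5.1% |
| 3, 30% | 4,000 and 6,000 | 0.977 | 0.957 | 6.0–6.9% | 5.5–6.4% | 5.1–5.5% |
| 10, none | 1,600 | 0.979 | 0.910 | 9.4–9.6% | 8.4–9.0% | 6.6% |

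Monte Carlo error is about 0.3–0.4 percentage points with three time points and up to 0.7 with ten. The ML/REML ratio agrees with the closed form at p = 5: √(115/120) = 0.979.

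**Step 3, why the time unit matters.** An unstructured matrix on T points has T(T + 1)/2 parameters: 6 for T = 3, 55 for T = 10, 1,830 for T = 60. The Measures section describes outcomes by POD 0–2, but injections and attempts were recorded hourly. At T = 10 the ML/REML ratio is still 0.979, so most of the 9% shortfall comes from uncertainty in the covariance matrix, which REML alone does not address. Sixty hourly points could hardly be fitted by either method in 120 children.

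**Step 4, the other reading of unstructured.** If the word refers only to the 2 × 2 matrix of a random intercept and slope, the ML standard error is about 2.1% below REML with 3 or with 10 time points.

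**Step 5, cost.** With three time points, intervals widen by 1/0.962 − 1 = 4.0% to 1/0.957 − 1 = 4.5%, before the small change in critical value. Nominal 80% power becomes Φ(1.960 + 0.842 − 1.960/ratio): 77.7% at 0.962, 77.5% at 0.957 and 74% at 0.910. Part of that lost power was spurious.

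**The case against.** The strongest reply is that the effect is too small to matter. On the POD reading it is one to two percentage points of type I error, it changes only borderline results, and it touches only two secondary-outcome models. All of that stands; it makes this a cheap improvement and not a serious defect.

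Four stronger readings are tempting, and the documents do not support them.
- *Selection used Wald p-values, so ML serves no purpose.* The plan gives a p-value criterion but names no test. With likelihood-ratio tests, ML is needed for that step, because REML likelihoods cannot compare models with different fixed effects.
- *The error is worst for the group comparison on POD 2.* The listed terms include no time-by-group interaction, so no POD 2 contrast is described. The number of children still on PCA that day is not given either.
- *REML with Kenward-Roger removes the problem at no cost.* It is close to nominal with three time points, but leaves about 6.6% with ten, and intervals widen.
- *The trial's main result is affected.* The primary outcome is the single satisfaction rating, which is not one of the modelled variables, and the simple group comparisons use a Mann-Whitney test. Neither depends on ML or REML.

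**Conclusion.** The point holds as a minor one. ML with an unstructured covariance and no stated small-sample correction gives a small bias towards significance in the two secondary-outcome mixed models. With three time points, the group-effect standard error is about 2–4% too small and type I error is about 6–7%. With ten it is about 9.5%. The sizes rest on an assumed time unit, within-child covariance, covariate mix and dropout; the direction does not. Only p-values near 0.05 would be affected on the POD reading. The p-values also remain subject to backward selection, which neither REML nor Kenward-Roger corrects.

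**What to change.** Report all estimates, intervals and p-values for the two final models from a REML fit with Kenward-Roger standard errors and degrees of freedom. In SAS 9.4, which the plan lists, these are METHOD=REML and DDFM=KR; the plan does not say whether SAS or SPSS fitted these models. If selection used likelihood-ratio tests, keep ML for that step only and refit the selected model by REML with Kenward-Roger. Alongside this, state the time unit, the selection test, and whether the unstructured matrix applies to the residuals or the random effects, since the size of the correction depends on the first and last of these.

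The cost is a change of options and one refit per model, with no new data. Intervals become about 4% wider with three time points and about 10% wider (1/0.910 − 1) with ten.
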